Data Collection. All infants will be assessed in their homes once per month (+ or - 5 days), from 3-6 months of corrected age until sitting onset (can maintain independent sitting > 30 s) or 9 months corrected age, whichever occurs first. We have chosen this as our intervention endpoint because 1) once sitting is established, the way in which infants use their legs shifts drastically (from mostly supine and some prone free movement to primary use as postural stability) and 2) if they are not sitting independently by 9 months corrected age it is straightforward clinically to identify significantly delay. The goal of our intervention is to get them on the "right track" early, not to provide intervention once a significant delay has occurred. We have chosen to start our intervention at 3 months of corrected age, as this is just before relationships have been observed between leg movement frequency and later functional outcomes (as described in the significance section). Sensor Data. To record leg movement rate, infants will wear custom leg warmers with a pocket that securely holds a movement sensor at each ankle from the morning visit until bedtime. The caregivers will remove the leg warmers and sensors when they put their infant to bed for the night (~10-12 hours later). We will return to pick them up the next day. Amount and type of leg movements will be determined using our existing, validated software algorithms. Assessments. We will measure the infant's weight, length, head circumference, thigh and shank lengths and circumferences. We will document medical and therapy interventions being received and assess motor skills using the Alberta Infant Motor Scale (AIMS), a standardized, norm-referenced observational scale¹⁶. We will record 5 minutes of spontaneous movement video to have a visual reference for data. We will record the caregiver teaching the child a novel task and assess the caregiver-infant interaction using the Nursing Child Assessment Teaching Scale (NCAT), a evidence based standardized-assessment tool¹⁷.

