Intervention. At each visit, the caregiver will be reminded of the infant's movement. The research team will spend 15 minutes interacting with the caregiver to determine possible ways to achieve the goal of 1200 movements per hour of awake time, with a variety of movements. Strategies to increase leg movements will be encouraged based on the infant's developmental level and what they demonstrate a response to, including: shake a toy when infant moves legs, sing a line of a song when infant moves legs, change the position of the infant to encourage more leg movement, or lightly tickle the legs and feet of the infant. The intervention will use the GAME (Goals - Activity - Motor Enrichment) protocol, a motor learning, environmental enrichment intervention that has recently been shown to be effective for improving motor skills in infants at high risk of cerebral palsy compared to standard care. The intervention is based on the principles of active motor learning, family centred care, parent coaching and environmental enrichment. Intervention was customised to parent goals and enrichment style and the child's motor ability. To increase the dose of motor practice families were provided with a home program containing suggested activities according to identified goals^{14,18,19}. We are expanding this effective intervention by applying it to a new population (infants broadly at risk as opposed to specifically at risk for cerebral palsy) and by specifically quantifying the dose of leg movement experience (amount and type). Otherwise, all intervention will be consistent with the established, published protocol. A customized logbook of all exercises with demonstration pictures of the baby, instructions, and tracking (amount and type) will be provided to the family each visit. Example Intervention Strategy. The research team and family determine that the baby likes Mom smiling and singing "You are my sunshine". They decide that every time the baby's diaper is changed, Mom will demonstrate by assisting the baby with

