producing alternating kicks while smiling and singing for 10 total alternating kicks (5 each leg) and then encouraging the baby to perform alternating kicks (not assisting) for 15 seconds and responding with singing and smiling if he or she does. Five sets will be performed each diaper change. Fidelity. Caregivers will keep logbooks of the amount and type of movement experience they provide. This will assist our efforts to create a manual of intervention strategies for future grant proposals. Despite best intentions, however, logbooks are often incomplete; the GAME study reported ~ 50% completion¹⁹. Our main fidelity measure in this study will be the movement rate and proportion of unilateral movements demonstrated by the infants across days and months. We will be able to compare these data to our existing observational data to measure the intervention effect size.

Follow Up: Families will be contacted by email or phone every 3-4 months from after the last visit until 24 months of corrected age for updates on their child's medical and developmental status.

Statistical test and analyses were performed using SPSS (Version 24; IBM, Corporation, Armonk, NY, USA). We first checked all variables for normality by plotting histograms and visually inspecting the data. Given the sample size and visual inspection of the variables, we chose to analyze our data using non-parametric statistics. The median and range were used to represent all descriptive statistics for the first and last visit. Wilcoxon Signed Ranked tests ($\alpha = 0.05$) were used to compare the leg movement rates, adherence, and NCAST-Teaching total score to test for significant differences between the first and last visits. Spearman rank order correlations ($\alpha = 0.05$) were used to test for significant relationships between quality of caregiver-child interaction and adherence to the intervention and leg movement rate at all visits.

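### The caregiver interaction score is an observer rating made by the study team that also coaches the families; no masking is described, so its secondary tests are open to observer bias of unknown size.

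*Combined protocol and SAP*

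**What the plan says.** Data Collection (Assessments) describes the measurement: "We will record the caregiver teaching the child a novel task and assess the caregiver-infant interaction using the Nursing Child Assessment Teaching Scale". The actor is the study team in the first person plural; no separate rater is named.

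The Intervention section says of each visit: "The research team will spend 15 minutes interacting with the caregiver to determine possible ways to achieve the goal". It adds: "The intervention is based on the principles of active motor learning, family centred care, parent coaching and environmental enrichment". The score therefore rates the behaviour of the person being coached. The team also supplies a logbook at each visit, and under Fidelity, "Caregivers will keep logbooks of the amount and type of movement experience they provide".

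The statistical paragraph after Follow Up uses the score twice. Wilcoxon signed-rank tests at the 0.05 level are "used to compare the leg movement rates, adherence, and NCAST-Teaching total score to test for significant differences between the first and last visits". At the same level, the plan then applies "Spearman rank order correlations" to look for "significant relationships between quality of caregiver-child interaction and adherence to the intervention and leg movement rate at all visits".

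Leg movement is measured differently: "Amount and type of leg movements will be determined using our existing, validated software algorithms".

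**The concern.** An observer rating can absorb what the rater knows or expects. Here three kinds of knowledge matter: which visit is being rated, how well the family has kept to the programme, and how much the infant's sensors recorded. Knowing the visit could shift the first-to-last comparison, most plausibly toward improvement. Knowing adherence or movement could produce part of the association that the correlations are meant to test.

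The study has one treated group, so masking here means masking to those three things, not to treatment arm. The first-to-last test has no concurrent control, so rating drift cannot be told apart from real change in caregivers. The score also enters every planned correlation. Because the episode is recorded, it can be scored without that knowledge, but the plan does not say that it is.

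**Working it through.** **1. Who rates, who coaches, what is masked.**
- Rating: the study team (Data Collection, Assessments).
- Coaching: the research team, 15 minutes per visit (Intervention).
- Masking to visit, adherence or movement: none described. Nor is there any shuffled scoring or agreement check.
- Blinding vocabulary appears only in the titles of cited studies in the reference list.
- Identifier codes (Potential Risks, Storage of Materials) separate data from personal identity. They are not described as hiding visit order or adherence.

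**2. The plan's own figure.** The sample size section claims 80% power for d = 1.0 with 12 against 24 infants at alpha 0.05. Normal approximation, two-sided:

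power = Φ(d / √(1/12 + 1/24) − 1.96) = Φ(1 / 0.3536 − 1.96) = Φ(0.868) = 80.7%.

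The two-sided t-test gives 78.5%. The figure reproduces, but it concerns sensor-measured leg movement and says nothing about the interaction score.

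**3. First-to-last test under an assumed drift.** The documents give no SD, so drift is expressed in SDs of the paired differences. With n = 12 the ranks sum to 12 × 13 / 2 = 78, and the exact two-sided test rejects when the smaller rank sum is 13 or less. Its attainable level is 174/4096 = 4.2%. Differences were drawn from a normal distribution with mean equal to the drift and SD 1, with no true change (200,000 simulated trials per row):

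| Assumed drift (SD) | Rejection rate |
|---|---|
| 0 | 4.2% |
| 0.2 | 8.3% |
| 0.3 | 13.8% |
| 0.5 | 31.5% |
| 0.8 | 66.7% |

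**4. Correlation under an assumed rater-induced association.** This takes one pair per infant (n = 12) and no true association (50,000 simulated trials per row). One pair per infant is an assumption: the plan correlates over all visits without saying how visits are pooled.

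| Induced correlation | Spearman rejection rate |
|---|---|
| 0 | 5.3% |
| 0.2 | 8.8% |
| 0.3 | 14.0% |
| 0.5 | 34.3% |

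Both tables show sensitivity to assumed inputs. Neither estimates the bias in this study.

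**The case against.** The strongest reply is that silence is not evidence of open scoring. No individual scorer is named and no time of scoring is given, and a recorded episode is consistent with later, masked scoring. The scale is described as standardised, it is not the primary outcome, and the study is a pilot of 12 infants. All of this stands. It limits the point to what the plan leaves open and keeps its weight low.

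A reader might also infer more than the text supports:
- *The coach rates her or his own families, visit by visit.* The overlap is documented only at team level, and no scoring schedule is stated.
- *The rater has reviewed the logbook.* The team supplies logbooks and caregivers keep them; no passage says they are read before scoring.
- *The rater knows that visit's leg movement rate.* Sensors are worn from the visit until bedtime and collected the next day. Someone scoring at the visit could know at most an earlier rate. The current rate could be known only if scoring came later.
- *A small uniform drift guarantees significance.* Twelve differences of one sign do give p = 2/4096, about 0.0005, but a 1-point drift forces this only if no caregiver's score varies otherwise. If the SD of the differences were 5 points (an assumption), a 1-point drift is 0.2 SD, and the rejection rate is about 8%.
- *The leg movement results are biased too.* That outcome comes from sensors and software.

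**Conclusion.** The point holds as a low-severity weakness in secondary analyses. The study team both assesses the interaction and coaches the caregiver, and the plan describes no masking to visit order, logbook adherence or sensor results. The first-to-last test of the score and its correlations with adherence and leg movement rate are therefore open to observer bias.

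Its size is unknown and its direction likely rather than certain. For assumed drifts of 0.2 to 0.5 SD, false rejection would rise from about 4% to between 8% and 32%. This rests on 12 complete pairs, normally distributed differences and no true change. The planned primary comparison of leg movement, 12 treated against 24 untreated infants, is not affected.

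**What to change.** After the last visit, score the existing teaching videos in one batch, under coded file names and in shuffled order across infants and visits, with no access to logbook or sensor results. Use those scores in the Wilcoxon and Spearman tests. Where the current team includes a member able to score who did not coach that family, use that member; no extra reader is required. The statistical paragraph is written in the past tense, so this may mean rescoring and repeating those tests. If scoring was already masked, state who scored and what they knew.

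The cost is coding the files and moving or repeating the scoring; no visit or procedure is added. There are two downsides. Scores arrive late. Masking is also partial, because the infant's age and some movement show on the video, so the first-to-last comparison is only partly protected. The main gain is masking to logbook adherence and to the sensor-measured rate. Caregivers' own reaction to being filmed and coached, and the lack of a concurrent control for this score, would remain.

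### The plan does not say whether caregiver-assisted kicks count towards the all-day leg movement rate; if they do, the comparison with untreated infants and with 1200 per hour is tilted modestly towards the intervention

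*Combined protocol and SAP*

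**What the plan says.** Under Data Collection (Sensor Data), "infants will wear custom leg warmers with a pocket that securely holds a movement sensor at each ankle from the morning visit until bedtime". The team's own previously validated software then determines the amount and type of movement. The software is not described further.

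Example Intervention Strategy first gives the occasion and who acts: "every time the baby's diaper is changed, Mom will demonstrate by assisting the baby with" a set of kicks. The content of one set is described as "producing alternating kicks while smiling and singing for 10 total alternating kicks (5 each leg". The caregiver then moves on to "encouraging the baby to perform alternating kicks (not assisting) for 15 seconds", and "Five sets will be performed each diaper change".

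The resulting rate has several uses:

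- Under Fidelity, the movement rate and the unilateral proportion are the main fidelity measures. The same paragraph adds: "We will be able to compare these data to our existing observational data to measure the intervention effect size".
- The statistical paragraph after Follow Up compares the rate between first and last visits with a Wilcoxon signed-rank test.
- Sample size justification names the primary comparison as leg movement in 12 treated against 24 untreated infants.
- The 1200 per awake hour threshold, taken from the team's pilot data, is the goal of the intervention.

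No section says that assisted movement is filtered out, that exercise periods are marked or cut, or that sensors come off during exercises. Potential Risks allows brief removal of the leg warmers, but only to inspect the skin.

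**The concern.** The worked example itself separates assisted kicks from kicks the infant makes unaided, but the outcome definition does not. A sensor at the ankle records the ankle moving, and nothing in the plan says that the software can tell who moved it. If assisted kicks are counted, a treated infant's rate can rise while the infant's own behaviour stays the same.

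This matters most where the other side of the comparison had no such exercise. The 24 untreated infants and the 1200 per hour threshold both come from observational data. Any counted assisted kicks are therefore added to the treated side only, and recruiting more infants would not remove a bias that runs one way. At stake is whether a higher rate shows that the infant moves more or partly reflects the caregiver carrying out the exercise.

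**Working it through.** **The plan's own figure.** Sample size justification states 80% power for d = 1.0 with 12 against 24 infants at alpha 0.05. Sidedness is not stated; I take it as two-sided.

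- Standard error in SD units: √(1/12 + 1/24) = 0.354.
- Normal approximation: Φ(1.0/0.354 − 1.96) = Φ(0.87) = 80.7%.
- Two-sided t-test: 78.5%, with d = 1.02 detectable at 80% power.

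The stated figure is reproduced.

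**Inputs from the documents.** 10 assisted kicks per set; 5 sets per diaper change; 15 unassisted seconds per set; sensors on both ankles for about 10 to 12 hours; target 1200 per awake hour.

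**Inputs assumed (not in the documents).** 3 to 10 diaper changes during wear; 5 to 12 awake hours; one count per assisted kick; software that does not reject assisted movement.

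**Gross addition.** Assisted kicks per change = 10 × 5 = 50. Addition per awake hour = 50 × changes / awake hours.

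| Case | Changes | Awake hours | Added per awake hour | Share of 1200 |
|---|---|---|---|---|
| Low | 3 | 12 | 150/12 = 12.5 | 1.0% |
| Central | 6 | 8 | 300/8 = 37.5 | 3.1% |
| High | 10 | 5 | 500/5 = 100 | 8.3% |

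If flexion and extension were counted separately, these figures would double.

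**Net of displaced movement.** While the legs are being moved, the infant is not kicking spontaneously. At 1200 per hour the spontaneous rate is 1200/3600 = 0.33 per second. At an assumed one second per assisted kick, 50 seconds displace about 17 kicks, so the net gain is about 33 per change. The central case becomes 33.3 × 6/8 = 25 per awake hour (2.1%). The range becomes 33.3 × 3/12 = 8.3 to 33.3 × 10/5 = 66.7 (0.7 to 5.6%).

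**Effect on the 12 versus 24 comparison.** The documents give no SD for the rate, so I assume 200 to 500 per hour, and that all 12 infants receive such an exercise. With b = gross addition / SD, the two-sided rejection probability when there is no true effect is Φ(b/0.354 − 1.96) + Φ(−b/0.354 − 1.96).

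| Gross addition | SD | b | Rejection probability |
|---|---|---|---|
| 37.5 | 500 | 0.08 | 5.5% |
| 37.5 | 200 | 0.19 | 8.3% |
| 100 | 500 | 0.20 | 8.7% |
| 100 | 200 | 0.50 | 29.3% |

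An artefact of d = 1.0 would need the high case together with an SD as small as 100 per hour.

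**The case against.** Several objections are sound and limit the point.

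- **The software may already reject assisted movement.** A reader might infer that the outcome does count caregiver-produced kicks. The documents support only that its handling is not stated.
- **Assisted kicks may be part of the intended dose.** The stated goal is to increase movement experience, and caregivers log what they provide. Counting assisted kicks for fidelity is therefore coherent. The objection does not extend to the rate as a measure of effect on the infant's own movement.
- **It is one illustration.** The strategies listed under Intervention (toy, song, change of position, light tickling) mainly prompt or reward the infant's own movement. How many of the 12 infants would receive assisted kicks is unknown, and the group-level artefact shrinks accordingly.
- **The first-versus-last test is less exposed.** A reader might infer equal bias there. Coaching takes place at every visit and recording starts from that visit, so the first recording may already contain the exercise and the bias may partly cancel.
- **The unilateral proportion.** It is tempting to say that assisted alternating kicks lower it. No section defines how alternating kicks are classified; if one leg moves while the other rests, they could raise it. The direction is not established.
- **Share of the gain.** A reader might express assisted kicks as a fraction of the movement that the exercise adds. That needs an infant kick rate for the 15-second windows, which the plan does not give, and treats one exercise as the whole gain. I give no such figure.

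What survives is the absence of a rule, together with a one-sided exposure in the comparison with untreated infants.

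**Conclusion.** The point holds in a limited form. The recording window overlaps an exercise that includes 50 assisted kicks per diaper change, and the plan does not say whether they count. If they do, infants given such a strategy gain about 12 to 100 gross movements per awake hour (1 to 8% of 1200), and somewhat less net of displaced kicks. The bias favours the intervention against the 24 untreated infants and against the threshold. These figures rest on the assumed diaper changes, awake hours and one count per kick.

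A reader might infer that the artefact could by itself produce the planned d of 1.0. The example does not support that: the central case is d = 0.08 to 0.19 under SDs of 200 to 500 per hour. This is a modest bias that is cheap to examine and does not undermine the pilot.

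**What to change.** State how the software treats assisted movement. If it already excludes it, that sentence closes the point. Otherwise:

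1. On the monthly recording days only, have caregivers mark start and end times of exercises in the logbook already supplied.
2. Keep the all-inclusive rate. Add, as a sensitivity analysis, a rate with marked exercise minutes removed from both the count and the awake-time denominator.
3. Report both against the 24 untreated infants and 1200 per hour, as an approximate upper and lower range for the infant's own rate. The reduced rate should not become the main measure: it also drops the unassisted kicks in the 15-second windows, and nothing says that caregiver play was removed from the observational data.
4. Report how many recordings lack marked times. Fidelity expects incomplete logbooks and cites about 50% completion in an earlier study.
5. Do not attribute to the infant's own movement an effect that appears only in the all-inclusive rate.

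The cost is one logbook line, a second run of existing software, a small caregiver burden, incomplete marking and a slightly less favourable second figure. At the assumed one second per assisted kick, each change removes 50 + 5 × 15 = 125 seconds, or about 6 to 21 minutes a day for 3 to 10 changes, not counting pauses between sets. The intervention itself is unchanged.

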questions. If they choose to participate after the initial contact, a written consent form will be mailed to them. This will allow the parents and/or legal guardians to discuss their participation with others before signing the written consent. 3) Research staff will attend the High Risk Follow-Up Clinic at CHLA. A licensed healthcare provider at CHLA, with the permission of the parent or legal guardian, will introduce the research staff to the family. The research staff will give more specific information about the study and answer any questions. If they choose to participate after the initial contact, a written consent form will be mailed to them. This will allow the parents and/or legal guardians to discuss their participation with others before signing the written consent. 4) A CHLA Clinical Research Coordinator (CRC) will coordinate with the High Risk Follow Up Clinic and potentially the NICU to review infants' medical records for eligibility and speak to families of potential participants. With the permission of the parent or legal guardian, the CRC will provide the research staff with the contact info. Research staff will call the parent or legal guardian and give more specific information about the study and answer any questions. If they choose to participate after the initial contact, a written consent form will be mailed to them. This will allow the parents and/or legal guardians to discuss their participation with others before signing the written consent.

Inclusion Criteria. Infants will be 3-6 months of adjusted age at the first visit, +/- 30 days. Infants will be defined as at risk in accordance with the definition below (confirmed by the PI or the CHLA CRC) ¹⁵:

CCS HRIF PROGRAM MEDICAL ELIGIBILITY CRITERIA

UPDATED 01/2017

Data should be collected on infants/children under three years of age who meet California Children's Services (CCS) HRIF medical eligibility criteria **and** who met CCS medical eligibility criteria for Neonatal Intensive Care Unit (NICU) care **OR** had a CCS eligible medical condition at some time during their stay in a CCS-approved NICU, even if they were never a CCS client. **Infants are medically eligible for the HRIF Program when the infant:**

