Sample size justification. We determined our sample size of 12 for this pilot intervention study based on our observational pilot data. In our pilot data, we found large effect sizes (Cohen's $d = 0.8 - 1.3$) for leg movement quantity (movements per hour of awake time) between 12 infants with TD and 24 infants AR (anticipate ~12 good and ~12 poor neuromotor outcomes). With the planned primary comparison of leg movement of those who received intervention ($N = 12$) versus those who did not ($N = 24$), we should be able to detect an effect of Cohen's d of 1.0 at 9 months, with $\alpha = 0.05$ and 80% power.

Potential Risks

Wearable Sensors: There is a small risk of skin irritation from wearing the legwarmers all day. Parents will be able to visually see their infants' feet at all times (they are not covered) and can remove the legwarmers briefly as desired to inspect their infant's skin. Although the movement sensors are small, they are not small enough to present a choking hazard. They measure 1.4 inches by 1.9 inches, larger than the standard choking hazard guidelines.²⁰

Storage of Materials. There is a small risk of disclosure of participant's personal information. Data collected from participants includes biological data of leg movement activity, video recordings and health status information. All information collected will be kept private and secure. Password protection and secure internal computer networks and REDCap, a HIPAA-compliant database system hosted by USC, will be used to collect and store data. Hard copies of data, including 2 backup copies on external hard drives, will be stored in a locked, waterproof, fireproof safe in a locked room in a secured building (keys, identification cards) on a secured campus (identification cards, security patrol). Unique identifier codes will be used to separate all data collected from any personal identifying information. Laboratory members will have access to data identified by code for analysis and manuscript preparation, while only the PI and Research Assistant (RA) will have access to identifying information for participant tracking purposes.

Intervention. As is typical with trying to get an infant to perform any desired behavior, there is a risk that

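### The powered primary comparison uses a non-randomised external cohort, but no between-group analysis is specified and nothing aligns the groups on age at recording, entry movement rate or eligibility

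*Combined protocol and SAP*

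**What the plan says.** All references are to the combined protocol and SAP.

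- **Fidelity:** of the treated infants' movement data, "We will be able to compare these data to our existing observational data to measure the intervention effect size".
- **Sample size justification:** the calculation opens "With the planned primary comparison of leg movement of those who received intervention", with 12 infants, against 24 who did not receive it. It concludes "we should be able to detect an effect of Cohen's d of 1.0 at 9 months", "with $\alpha = 0.05$ and 80% power". The pilot contrast was "between 12 infants with TD and 24 infants AR (anticipate ~12 good and ~12 poor neuromotor outcomes"), so the 24 untreated infants match the at-risk part of the pilot cohort.
- **Statistics paragraph (after Follow Up):** Wilcoxon signed-rank tests between first and last visits, and Spearman correlations of caregiver-child interaction with adherence and movement rate. There is no between-group test or model.
- **Inclusion Criteria:** "Infants will be 3-6 months of adjusted age at the first visit, +/- 30 days".
- **Data Collection:** "We have chosen to start our intervention at 3 months of corrected age". Significance also describes the intervention as running from 3 months. Visits are monthly and end at independent sitting or at 9 months corrected age, whichever comes first.

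The documents do not give the observational cohort's eligibility rules, enrolment period, ages at recording, follow-up rule or entry movement rates.

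**The concern.** A control group from an earlier study can differ from the treated group in ways unrelated to treatment. If the analysis does nothing about this, a prior difference cannot be told apart from an intervention effect, in either direction. The protocol itself gives reasons to care about two of the alignment variables:

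- **Movement rate.** Significance reports that at-risk infants below 1200 movements per awake hour more often have a poor neuromotor outcome. Rate is thus treated as prognostic, but it is neither an entry criterion nor a covariate in the primary comparison.
- **Age and stage.** Data Collection says that leg use changes sharply once sitting is established. A contrast that ignores age at recording could mix infants before and after that change.

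At stake is the effect size that the pilot is meant to supply. The only specified test of movement rate, the within-infant one, cannot supply it, because it does not separate the intervention from maturation.

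**Working it through.** **1. Reproduce the stated power.** Inputs from Sample size justification: n = 12 and 24, d = 1.0, alpha 0.05. Sidedness is not stated; two-sided is assumed.

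- Standard error of the difference in SD units: sqrt(1/12 + 1/24) = 0.354.
- Noncentrality: 1.0 / 0.354 = 2.83.
- Normal approximation: Phi(2.83 - 1.96) = 80.7%.
- Noncentral t, 34 df: 78.5%.

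The stated 80% stands. It rests on exchangeable groups that are all observed at 9 months.

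**2. Can the 9-month contrast be run as written?** Entry runs from about 2 months (3 months minus 30 days) to about 7 months (6 months plus 30 days). Time from entry to 9 months is therefore 9 - 7 = 2 to 9 - 2 = 7 months, and less for infants who sit earlier. A 9-month recording exists only for infants not yet sitting at the preceding visit. Their number is not given. If k of 12 have one and all 24 controls do, power at d = 1.0 (noncentral t) is:

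| k | Power |
|---|---|
| 10 | 73.1% |
| 8 | 65.9% |
| 6 | 56.2% |
| 4 | 43.0% |

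If the last visit is used instead, treated recordings fall at varying ages, and nothing says how the cohort's recordings would be matched to them.

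**3. Effect of a pre-existing difference.** Let b be the difference in SD units that would exist without intervention. The documents do not give b; the values are assumptions. Noncentrality is b / 0.354 for the null case and (1 - b) / 0.354 when the difference runs against a true d of 1.0.

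| b | Two-sided rejection, no true effect | Power at true d = 1.0, opposing b |
|---|---|---|
| 0 | 5.0% | 78.5% |
| 0.2 | 8.5% | 59.4% |
| 0.3 | 13.1% | 48.6% |
| 0.5 | 28.0% | 28.0% |

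For scale, the pilot differences between typically developing and at-risk infants were 0.8 to 1.3 SD. Those are different populations, so they do not estimate b.

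**4. What alignment would do to power.**

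- Adjusting for entry rate with correlation r to the later rate multiplies the residual SD by sqrt(1 - r^2). At r = 0.5 the effective d is 1 / sqrt(0.75) = 1.15 and power is 88.7%; at r = 0.3 it is 82.1%. Here r is assumed, all 24 controls are kept, and one covariate is fitted with the groups otherwise balanced.
- If restriction or matching leaves 12 versus 12, the standard error is sqrt(2/12) = 0.408. Unadjusted power at d = 1.0 is 64.9% (t) or 68.8% (normal). The effect detectable with 80% power becomes (1.96 + 0.842) x 0.408 = 1.14 SD by the normal approximation, against 2.80 x 0.354 = 0.99 now.

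**The case against.** The strongest reply is that this is a before-and-after pilot. Its specified test uses each infant as its own baseline, and the external comparison already shares an at-risk label and a nominal age of 9 months. Silence about the cohort does not show misalignment. All of that is accurate. It does not remove the gap, because the external contrast is the one called primary, powered and intended to measure the effect, and it has no stated method.

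Several stronger readings are tempting but unsupported:

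- **That raw values will be compared, or that the groups are known to differ.** The plan gives no method at all, and the cohort is not described.
- **That first-visit rate goes unused.** It enters the within-infant Wilcoxon test; it is absent only from the between-group comparison.
- **That a chance imbalance is bias.** With an even mix of infants with later good and poor outcomes, a split of 8 or more, or 4 or fewer, of 12 has probability 2 x (0.121 + 0.054 + 0.016 + 0.003) = 0.39. This is sampling variation, already covered by the standard error and alpha.
- **That the cohort was classified under older risk criteria.** The criteria are marked 01/2017 and the citation was accessed in 2014. That may be only a stale reference and says nothing about the cohort.
- **That families recruited by flier differ.** Fliers are part of one of four routes, and the cohort's recruitment is not described.

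One objection changes the remedy. Sensors go on at the morning visit and caregivers are coached at each visit, with no exemption for the first. The first recording may therefore already reflect coaching, and adjusting for it could remove part of the effect.

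**Conclusion.** The point holds as a gap in the primary comparison: an external, non-randomised control is to measure the effect, with no stated between-group analysis and no alignment on age at recording, entry rate or eligibility. The 9-month time point also does not fit a visit schedule that can end earlier. The sample size arithmetic is sound.

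Neither the sign nor the size of any bias can be derived from the documents. The rise from 5% to about 13% to 28% rests on an assumed difference of 0.3 to 0.5 SD, a two-sided t-test and all 36 infants being observed. The gain to 88.7% from adjustment is equally conditional and should not be presented as the expected result. Variable entry age alters months of intervention; it does not by itself confound a contrast made at a common age. This is a change that should be made before the effect size is used to plan further work.

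**What to change.** In the statistics paragraph and Sample size justification:

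1. Describe the observational cohort: eligibility, enrolment period, ages at recording and follow-up rule.
2. Specify the between-group analysis. Use the observational recording at the corrected age closest to each treated infant's recording, adjusted for first-visit movement rate and corrected age; or compare change over matched age intervals.
3. Restrict controls to infants who meet this protocol's at-risk definition and leg-malformation exclusion.
4. State whether the first recording precedes any effect of coaching. Use it as a baseline only if it does; otherwise report the analysis with and without that adjustment.
5. Label the result a non-randomised contrast, and descriptive only if the cohort lacks early recordings.
6. Report months of intervention per infant. Reconcile the 3-month start in Significance and Data Collection with the entry window in Inclusion Criteria, and the 9-month time point with the end-of-visits rule.

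The cost is analysis wording and a re-check of 24 existing records. Some controls may be lost, so the detectable effect must be restated for the number left. If only 12 versus 12 remain, unadjusted power at d = 1.0 is about 65%.
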